3.2 Randomization

For Monotherapy Phase 2, up to 75 subjects will be enrolled per dose level using a randomized (if 2 or more doses), parallel cohort, non-comparative (estimation) design.

The Combination Phase 2 portion will follow a randomized, parallel group, non-comparative design, assuming both the RP2D and the lower dose are investigated, or a single dose cohort, if only the RP2D is investigated. Approximately 56 subjects will be enrolled in each dose cohort. Each dose cohort will follow a Simon 2-stage design.

3.3 Hypothesis Testing

All statistical analyses will be descriptive in nature and no formal hypothesis testing will be performed. Phase 1 statistical methodology will be applied towards identification of the MTD and for Phase 2 towards estimation of anti-tumor activity.

3.4 Interim Analysis

Interim futility analyses will be conducted between stages during the Combination Phase 2. The guiding futility and promising criteria for the combination cohort are presented in [Table 1](#).

Statistical Analysis Plan

Protocol No. ZN-c5-001

Revision 00: 17Feb2023

(Page 15 of 47)

Table 1 Sample Size Assumptions and Criteria for Simon's Two-Stage Design

	CBR Assumptions		2-Stage Sample Size	Stage 1 Futility Criteria
	Poor	Promising		
ZN-c5 Combination			1-sided 0.025 alpha level 80% power	
+ Palbociclib	50%	70%	51 evaluable subjects (approximately 56 total)	≤ 10 of 19 (53%)

3.5 Sample Size

3.5.1 Monotherapy Dose Escalation and Combination Dose Escalation

The primary objective of this part of the study is to identify the MTD, if possible, or the RP2D of ZN-c5 as monotherapy and in combination with palbociclib, and to recommend dose(s) for evaluation in future clinical studies. Hence, the number of subjects in the cohorts has been based on the desire to obtain adequate tolerability, safety and PK and pharmacodynamics data while exposing as few subjects as possible to the investigational product and procedures.

For the Monotherapy Dose Escalation phase of the study, cohorts of 3-6 evaluable subjects will be required. The total number of subjects will depend upon the number of dose escalations necessary, but it is estimated to be approximately 36 subjects.

The Combination Dose Escalation with palbociclib will be initiated at a dose deemed well-tolerated in the Monotherapy Dose Escalation and proceed with higher ZN-c5 doses, as tolerated, based again on the standard rules of a 3+3 design (protocol section 6.1.4). The total number of subjects will depend upon the number of dose escalations necessary, but it is estimated to be approximately 40 subjects (including alternate dosing schedules, e.g., BID, and possible backfill). The subjects in the Combination Dose Escalation might also count towards the futility assessment stage accrual in the Combination Phase 2 (protocol section 6.1.7, Combination Phase 2).

3.5.2 Monotherapy Expansion

The Monotherapy Expansion will be initiated at a dose selected based on PK, safety and any available biomarker data from the ZN-c5 Monotherapy Dose Escalation at a specific dose level will continue until a higher dose has been deemed to be well-tolerated (no DLTs in 3 subjects or at most 1 DLT in 6 subjects in the Monotherapy Dose Escalation), at which point expansion accrual might shift to the higher dose level.

The CBR as measured using RECIST v.1.1 will be assessed to provide preliminary anti-tumor activity evaluation in a subject population thought most likely to respond to ZN-c5.

The Monotherapy Expansion overall will target balanced accrual between the 3 lines of therapy (1st, 2nd and 3rd hormonal therapy line) across dose levels. The total cohort size necessary for futility has been estimated based on futility screening criteria targeting 10 evaluable subjects per line cohort at dose levels where any anti-tumor activity is demonstrated and providing an acceptable false negative risk of concluding that there is no activity if the true clinical benefit rate is at least 40%.

Statistical Analysis Plan

Protocol No. ZN-c5-001

Revision 00: 17Feb2023

(Page 16 of 47)

Subjects are evaluable for the CBR if they have at least 1 post baseline disease/tumor assessment (protocol section 9.3). CBR as measured using RECIST v.1.1 will be assessed to provide preliminary anti-tumor activity evaluation in a subject population thought most likely to respond to ZN-c5. Data from these cohorts will provide a preliminary assessment of anti-tumor activity based on CBR.

The total number of subjects in all expansion cohorts will depend upon the number of dose escalations, but it is not estimated to exceed 45 subjects.

3.5.3 Monotherapy Phase 2

Up to 3 dose levels with up to 75 subjects per dose level will be enrolled using a randomized (if 2 or more doses), parallel cohort, non-comparative (estimation) design.

Efficacy in the Monotherapy Phase 2 will be assessed as in the Monotherapy Expansion and CBR outcomes in the Monotherapy Phase 2 will be combined with those from subjects in the Monotherapy Expansion arm who were treated with ZN-c5 as 2nd/3rd Line of treatment and dosed at the same ZN-c5 dose in the Monotherapy Expansion. The sample size is determined in order to estimate the CBR at each dose level with certain confidence before proceeding with a larger confirmatory study. Based on the targeted sample size, the precision for a 95% exact confidence interval around a hypothesized 40 – 50% CBR rate is $\pm 12\%$ at each dose level studied.

Historical estimates for the CBR rate specific to 2nd/3rd Line subjects (either post CDK4/6 inhibitor or not) are not readily available. The CBR range was estimated based on two studies, reporting a CBR rate for fulvestrant alone of 40% in 2nd Line or higher (PALOMA-3) and 56% CBR in 1st or 2nd Line (MONARCH-2). The targeted precision will be adequately achieved within the specified range and it will increase further outside of the range, if the true CBR rate is further (higher or lower) from 50%.

3.5.4 Combination Phase 2

The Combination Phase 2 portion follows a randomized, parallel group, non-comparative design, assuming both the RP2D and the lower dose are investigated, or a single dose cohort, if only the RP2D is investigated. Each dose cohort is independently powered (non-comparative) and follows a Simon 2-stage design.

Approximately 56 subjects will be enrolled in each dose cohort. Subjects treated in the Combination Dose Escalation at lower doses can possibly also count towards the futility stage accrual, assuming the subjects are evaluable. The two dose cohorts evaluated in Phase 2 will not use the same subjects from lower dose cohorts in the Phase 1 Combination Dose Escalation phase; for example, ZN-c5 50 mg Combination Dose Escalation subjects may count for the 100 mg futility cohort in Phase 2, if that is selected as the lower dose cohort for the Phase 2 component but will not also count for the RP2D futility cohort, if a higher dose is selected as the RP2D.

CBR as measured using RECIST v.1.1 will be assessed to provide preliminary anti-tumor activity evaluation in a subject population thought most likely to respond to ZN-c5. Subjects are evaluable for CBR if they have at least 1 post baseline disease/tumor assessment (protocol section 9.3).

Sample size for each dose cohort is based on a Simon 2-stage design with 80% power at the 1-sided 2.5% alpha level to differentiate between 50% CBR (poor performance) and 70% CBR (promising performance). Fifty-one (51) evaluable subjects will be enrolled in two stages, with 19 subjects in Stage 1 and 32 subjects in Stage 2. The probability of early stopping is 68%. The Combination Phase 2 will target balanced accrual between the 2 lines of prior hormonal therapy (1st and 2nd hormonal therapy line) across dose levels.

Second stage accrual will be completed, assuming that Stage 1 futility criteria are exceeded with at least 11 subjects with CBR in the first 19 evaluable subjects, as outlined in [Table 1](#). An approximate 10% loss for CBR evaluability has been assumed resulting in a sample size of approximately 56 subjects for each cohort, resulting in a total sample size of approximately 112 subjects for this trial stage.

3.6 Study Procedures

All subjects will be assessed by scheduled clinical, laboratory and other diagnostic assessments throughout the study. All efforts should be made to perform assessments as close as possible to the scheduled time points. Visit windows are provided below in [Table 2](#). Study assessments are to be performed as follows:

- Screening evaluations are to be performed within 28 days prior to first study drug dose.
- The day of first administration of study drug will be considered Day 1 of study.
- Cycle 1 Day 1, Cycle 1 Day 2, Cycle 1 Day 16 should be conducted on the day of, there is no window allowed. Cycle 1 Day 8 may be conducted \pm 1 day, Cycle 1 Day 15 may be conducted \pm 2 days.
- Day 1 evaluations for Cycles \geq 2 may be conducted \pm 4 days; Day 15 evaluations for Cycle 2 (only for subjects participating in Combination Therapy) may be conducted \pm 2 days. In the Combination Dose Escalation and Combination Phase 2 with palbociclib, the window for the Day 1 visit for subsequent cycles is only $+ 4$ days, since there must always be at least a full 7-day off treatment recovery period for palbociclib before starting the next 21-day dosing cycle.
- Tumor assessments should be performed every 8 weeks (\pm 7 days) after Cycle 1 Day 1 for the first 24 weeks. After 24 weeks, scans may be performed every 12 weeks (84 days) \pm 7 days, and at the time of discontinuation (if not performed within the last 4 weeks \pm 7 days).
- End of Treatment assessments should be performed within 7 days from discontinuation of study drug.
- Safety follow-up assessments should be performed 30 days \pm 7 days after the last administration of study drug, and prior to the start of new anticancer treatment.
- Disease assessment follow-up assessments should be conducted every 12 weeks (84 days) \pm 7 days for subjects without disease progression (PD) at the time of study drug discontinuation until confirmation of PD, initiation of the first subsequent anticancer therapy, withdrawal of consent, death, loss to follow-up or until the study is terminated, whichever occurs first. Survival follow-up should be conducted every 12 weeks (84 days) \pm 14 days from the time disease progression is confirmed or the first subsequent new breast cancer therapy is initiated.

3.7 Schedule of Assessments

Table 2 Time and Events Schedule

Study Phase	Screening	Cycle 1 (28-day cycle)					Cycles \geq 2 (28-day cycle)		EOT	30-day Safety Follow-up	Disease Assessment Follow-up ²¹ (every 12 weeks)	Survival Follow-up ²² (every 12 weeks)
Cycle Day	Day -28	Day 1	Day 2	Day 8	Day 15	Day 16	Day 1	[Day 15* Cycle 2 Combination only]				
Window (days)	-28 to -1			± 1	± 2		$[\pm 4^{23}]$	$[\pm 2]$	± 7	± 7	± 7	± 14
Informed Consent	X											
Medical and Medication History ¹	X											
Physical Examination ²	X	X		X	X		X	[X]	X	X		
ECOG Performance Status	X	X					X	[X]	X	X		
Vital Signs ³	X	X		X	X		X	[X]	X	X		
TriPLICATE 12-lead ECG ⁴	X	X	[X]		X	[X]	[X]		X			
Adverse events/ Concomitant medications ⁵	[X]	X	[X]	X	X	[X]	X	[X]	X	X		
Enrollment	X											
Hematology	X ⁷	X		X	X		X	[X]	X	X		
Chemistry	X ⁷	X		X	X		X	[X]	X	X		
Coagulation ⁸	X ⁷								X			
Full Lipid Panel ⁹		[X]					[X]					

Study Phase	Screening	Cycle 1 (28-day cycle)					Cycles ≥ 2 (28-day cycle)		EOT	30-day Safety Follow-up	Disease Assessment Follow-up ²¹ (every 12 weeks)	Survival Follow-up ²² (every 12 weeks)
Cycle Day	Day -28	Day 1	Day 2	Day 8	Day 15	Day 16	Day 1	[Day 15* Cycle 2 Combination only]				
Window (days)	-28 to -1			± 1	± 2		[± 4 ²³]	[± 2]	± 7	± 7	± 7	± 14
Urinalysis ¹⁰	X ⁷								X			
Pregnancy Test ¹¹	X	X					X		X	X		
PK ¹²		[X]	[X]	[X]	[X]	[X]	[X]					
ZN-c5 pharmacodynamic and exploratory biomarkers in blood ¹³		X					X		[X]		[X]	
Tumor Biopsy ¹⁴	[X]						[X]		[X]		[X]	
ESR1 Mutation ¹⁵		X					X		[X]		[X]	
CT/MRI ¹⁶	X						X		X		[X]	
4β-hydroxycholesterol / cholesterol ¹⁷		X			X		X					
FES-PET ¹⁸	[X]						[X]					
ZN-c5 oral dosing ¹⁹		X										
Palbociclib oral dosing (Combo only) ²⁰		[X]										

Study Phase	Screening	Cycle 1 (28-day cycle)					Cycles ≥ 2 (28-day cycle)		EOT	30-day Safety Follow-up	Disease Assessment Follow-up ²¹ (every 12 weeks)	Survival Follow-up ²² (every 12 weeks)
		Day -28	Day 1	Day 2	Day 8	Day 15	Day 16	Day 1				
Cycle Day	Day -28	Day 1	Day 2	Day 8	Day 15	Day 16	Day 1	[Day 15* Cycle 2 Combination only]				
Window (days)	-28 to -1			± 1	± 2		[± 4 ²³]	[± 2]	± 7	± 7	± 7	± 14
Subject Dosing Diary Accountability and/or Dispensing ⁶		X					X		X			
LTFU ²²												[X]

Notes: X = Required; [X] = Only applicable as per footnote as indicated by the Assessment

Cycle 1 Day 1 safety lab samples, physical examination, ECOG status and pregnancy test may be assessed up to 3 days prior to the Day 1 visit. On subsequent visits throughout the study, these procedures/assessments are allowed to be performed within 1 day prior to the planned visit.

Cycle 1 Days 2 and 16 are only required for subjects participating in the Phase 1 parts of the protocol.

*Cycle 2 Day 15 visit – only for subjects participating in Combination Therapy (Combination Dose Escalation and Phase 2)

Please refer to Section 8 for details on changes on data collection after the specific cut-off date.

1. Medical history includes significant past medical events (e.g., prior hospitalizations or surgeries), a review of the disease under study, prior anti-cancer therapies, and any concurrent medical illnesses.
2. Screening and End of Treatment Physical Examinations (PE) will be a complete PE. Beginning at C1D1, a modified physical examination may be performed. Weight (without shoes) should be measured at each PE. Height (without shoes) is measured at Screening only.
3. C1D1 Vital Signs will be taken within 15 min pre-ZN-c5 dose and 2 and 4 hours post-dose (Phase 1) or pre-dose and 2 hours post-dose (Phase 2); vital signs will be taken pre-dose only at all subsequent visits. Oxygen saturation will be tested with a pulse oximeter.
4. Resting, semi recumbent triplicate ECGs will be collected at any time during Screening window, Day 1 of every other cycle (alternating cycles) starting with Cycle 2 (at pre-dose), and at EOT. In Phase 1, triplicate ECGs will be collected on C1D1 and C1D15 at pre-dose, 8 hours, and 24 hours post-dose (pre-dose on C1D2 and C1D16). In Phase 2, triplicate ECGs will be collected on C1D1 and C1D15 at pre-dose and 2 hours post-dose. ECGs should preferably be collected prior to PK (or any other blood draw) if they are to be collected at the same nominal time point. ECGs should be collected over a 5 minute window at each time point.

5. AEs will be assessed using NCI CTCAE (v 4.03) criteria. Subjects will also return to clinic at 30-days (\pm 7 days) post last IP dose (but prior to initiation of subsequent breast cancer therapy) to assess AEs and SAEs. At Screening, all medications taken up to 30 days prior to Screening will be documented in the eCRF.
6. Subjects will be given a Subject Diary on which they will record dates/times of study drug administration. Compliance with study drug(s) will be assessed and reviewed during visits.
7. Screening chemistry, hematology, coagulation, and urinalysis should be collected within 7 days of C1D1.
8. Coagulation assessment includes PT/INR, aPTT.
9. A non-fasting full lipid panel will be performed on C1D1, C3D1 (coinciding with the first on-study tumor assessment after 8 weeks) and C7D1 (6 months into the study). This will not be collected in the Monotherapy Phase 2.
10. Urinalysis assessment includes visual inspection, microscopic examination, and dipstick test for pH, protein, glucose, WBC, bilirubin, and blood.
11. Serum pregnancy testing will be conducted at Screening (within \leq 7 days of C1D1). Serum or urine pregnancy tests thereafter will be done on Day 1 of every cycle for all premenopausal and perimenopausal female subjects of childbearing potential, including EOT and the Safety Follow-up Visit.
12. Plasma samples for PK analysis of ZN-c5 (having been administered without food [at least 1 hour before and 2 hours after a meal]) and of palbociclib (having been administered with food) will be collected relative to ingestion of each drug as per Protocol Table 6 and Table 7. Regarding the PK sampling for ZN-c5 if administered twice daily (BID), a sample at 12 hours post morning dose and immediately preceding the second daily dose may also be collected (optional). Note: If the optional, On-Treatment tumor biopsy is performed, an additional PK sample should be collected at that time.
13. Whole blood, serum and/or plasma will be collected for exploratory biomarkers at C1D1, C2D1, and at time of disease progression.
14. Tumor biopsy: At baseline, de novo biopsy of any amenable site of disease (at investigator's discretion). Additional tumor biopsy at C2D1 or any time beyond may also be obtained. The on-treatment biopsy should be obtained 2 – 4 hours after the subject has taken the ZN-c5 dose that day. Subjects will also have the option to undergo a biopsy of a lesion at the time of disease progression. Samples will be collected, labelled, stored and shipped as detailed in the laboratory manual. Any residual tumor remaining after analysis may be used for exploratory research into factors that may influence development of breast cancer and/or response to ZN-c5. All tumor biopsies are optional for all subjects participating during the study. Biopsies must not be taken from target lesions used to assess anti-tumor efficacy, if possible. If sufficient tumor material is available, part of the tumor biopsy at C2D1 will be used for determination of ZN-c5 tissue concentration. If a biopsy is obtained on C2D1 or beyond, a plasma PK sample should also be collected, as close as possible, within 2 hours prior to the biopsy.
15. A blood sample for the assessment of ESR1 mutations will be drawn at C1D1, C2D1, and at time of progression.
16. Tumor evaluation by CT/MRI or applicable scan will be performed during Screening (within 28 days of Cycle 1 Day 1) and every 8 weeks (\pm 7 days) after C1D1 for the first 24 weeks. After 24 weeks, scans may be performed every 12 weeks (\pm 7 days). The same radiographic

procedure used to define measurable lesions must be used throughout the study for each subject. Applicable scans to be done at EOT visit if not done within the previous 4 weeks.

17. Plasma samples for 4 β -hydroxycholesterol and cholesterol will be collected pre-dose on C1D1, C1D15, and pre-dose on Day 1 of Cycles 2-4 of the Monotherapy Dose Escalation and Expansion.
18. A FES-PET scan (optional) should be conducted at Screening and at least after 1 month of treatment (preferably within the first 2 months, in Cycle 2).
19. Beginning on C1D1, subjects will take ZN-c5 once daily (alternatively, this total daily dose may be divided by 2 and administered BID [every 12 hours]). ZN-c5 dosing and administration as per assigned cohort (see Section 6.1.2.1).
20. In Phase 1, beginning on C1D1, subjects in the combination treatment cohorts will take palbociclib at the label indicated dose of 125 mg orally once daily (2 hours after the ZN-c5 dose was taken) for 21 consecutive days followed by 7 days off treatment (1 cycle of treatment = 28 days) (see Section 6.1.2.2). In Phase 2, subjects in the combination treatment cohorts will take palbociclib at the label indicated dose of 125 mg orally once daily (at the same time the ZN-c5 dose is taken) for 21 consecutive days followed by 7 days off treatment (1 cycle of treatment = 28 days).
21. Disease Assessment Follow-up Visit: Subjects without progression of disease (PD) at the time of study drug discontinuation will continue to undergo disease evaluations every 12 weeks \pm 7 days until confirmation of PD, initiation of the first subsequent cancer therapy, withdrawal of consent, death, loss to follow-up, or until the study is terminated. Once a subject has confirmation of PD or has initiated subsequent cancer therapy, whichever occurs first, disease follow-up will discontinue.
22. Long-term Follow-up (LTFU) – Subjects will be contacted every 3 months (phone or medical records) for survival status and collection of subsequent breast cancer treatments.
23. In the Combination Dose Escalation and Combination Phase 2 with palbociclib, the window for the Day 1 visit for subsequent cycles is only + 4 days, since there must always be at least a full 7-day off treatment recovery period for palbociclib before starting the next 21-day dosing cycle.

4. DATA AND ANALYTICAL QUALITY ASSURANCE

The overall quality assurance procedures for the study data, statistical programming and analyses are described in Everest's Standard Operating Procedures. Detailed data management procedures are documented in the Data Management Plan, Data Validation Check Specifications, and Safety Data Review Plan. Detailed statistical and programming quality control and quality assurance procedures are documented in the Statistical Analysis and Programming QC/QA Plan.

The study endpoints and analytic approaches are both prospectively defined and documented in the protocol and in this SAP. The SAP will be finalized prior to the database lock and data analysis.

5. ANALYSIS POPULATIONS

5.1 Full Analysis Set (FAS)

The FAS includes all subjects who receive ≥ 1 dose of study drug. This analysis set will be used for subject characteristics and efficacy endpoints.

5.2 Tumor Response Evaluable Set

The Tumor Response Evaluable Set includes all subjects in the FAS with at least 1 evaluable post-baseline response assessment using RECIST 1.1. Subjects who develop PD, intolerable toxicity or death or who discontinue study treatment prior to the first post-baseline assessment will also be considered evaluable and will be classified as non-responders. This analysis set will be used for futility assessment in the Phase 2 combination (if that part is executed) as well as a supportive population in the analysis of efficacy endpoints involving tumor response data. Objective response rate will be assessed in the subset of subjects with measurable disease at baseline.

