- 16. Tumor evaluation by CT/MRI or applicable scan will be performed during Screening (within 28 days of Cycle 1 Day 1) and every 8 weeks (± 7 days) after C1D1 for the first 24 weeks. After 24 weeks, scans may be performed every 12 weeks (± 7 days). The same radiographic procedure used to define measurable lesions must be used throughout the study for each subject. Applicable scans to be done at EOT visit if not done within the previous 4 weeks.
- 17. Plasma samples for 4β -hydroxycholesterol and cholesterol will be collected pre-dose on C1D1, C1D15, and pre-dose on Day 1 of Cycles 2-4 of the Monotherapy Dose Escalation and Expansion.
- 18. A FES-PET scan (optional) should be conducted at Screening and at least after 1 month of treatment (preferably within the first 2 months, in Cycle 2).
- 19. Beginning on C1D1, subjects will take ZN-c5 once daily (alternatively, this total daily dose may be divided by 2 and administered BID [every 12 hours]). ZN-c5 dosing and administration as per assigned cohort (see Section 6.1.2.1).
- 20. In Phase 1, beginning on C1D1, subjects in the combination treatment cohorts will take palbociclib at the label indicated dose of 125 mg orally once daily (2 hours after the ZN-c5 dose was taken) for 21 consecutive days followed by 7 days off treatment (1 cycle of treatment = 28 days) (see Section 6.1.2.2). In Phase 2, subjects in the combination treatment cohorts will take palbociclib at the label indicated dose of 125 mg orally once daily (at the same time the ZN-c5 dose is taken) for

- 21 consecutive days followed by 7 days off treatment (1 cycle of treatment = 28 days).21. Disease Assessment Follow-up Visit: Subjects without progression of disease (PD) at the time of study drug discontinuation will continue to undergo disease evaluations every 12 weeks \pm 7 days until confirmation of PD, initiation of the first subsequent cancer therapy, withdrawal of consent, death, loss to follow-up, or until the study is terminated. Once a subject has confirmation of PD or has initiated subsequent cancer therapy, whichever occurs first, disease follow-up will discontinue.
- 22. Long-term Follow-up (LTFU) Subjects will be contacted every 3 months (phone or medical records) for survival status and collection of subsequent breast cancer treatments.

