Up to 75 subjects will be enrolled per dose level using a randomized (if 2 or more doses), parallel cohort, non-comparative (estimation) design. Efficacy in the Monotherapy Phase 2 will be determined by CBR and results will be combined with those from subjects with similar treatment characteristics (2nd/3rd Line therapy) and treated at the same dose level of ZN-c5 in the Monotherapy Expansion arm (Section 9.2.3). Therefore, the targeted total N (Phase 2 and same population/dose subjects in the Monotherapy Expansion combined) is 75 subjects per dose level to estimate the CBR rate with certain confidence before proceeding with a larger confirmatory study.

6.1.8 COMBINATION PHASE 2

Following the determination of the MTD/RP2D for ZN-c5 in combination with palbociclib, additional subjects will be enrolled to further assess the safety, tolerability, and preliminary efficacy of ZN-c5 in combination with palbociclib.

ZN-c5 will be administered at the combination RP2D and potentially at a lower dose in combination with palbociclib. The lower ZN-c5 dose will be selected based on available safety, PK and biomarker data.

Efficacy in the Combination Phase 2 will be determined by CBR. The Combination Phase 2 will target balanced accrual between the 2 lines of therapy (1st and 2nd hormonal therapy line) across dose levels.

The Combination Phase 2 portion will follow a randomized, parallel group, non-comparative design, assuming both the RP2D and the lower dose are investigated, or a single dose cohort, if only the RP2D is investigated. Each dose cohort will follow a Simon 2-stage design.

Approximately 56 subjects will be enrolled in each dose cohort. Subjects treated in the Combination Dose Escalation at a demonstrated well-tolerated lower combination dose (no DLTs in 3 subjects or at most 1 DLT in 6 subjects) may also count towards the futility stage accrual, assuming the subjects are evaluable (dosed subjects with at least 1 post baseline disease/tumor assessment [Section 9.3]). The two dose cohorts evaluated in Phase 2 will not use the same subjects from lower dose cohorts in the Phase 1

Combination Dose Escalation phase; for example ZN-c5 50 mg Combination Dose Escalation subjects may count for the 100 mg futility cohort in Phase 2, if that is selected as the lower dose cohort for the Phase 2 component, but will not also count for the RP2D futility cohort, if a higher dose is selected as the RP2D.

Futility (Stage 1) and Efficacy (Stage 2)

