7.2 PARTICIPANT DISCONTINUATION/WITHDRAWAL FROM TREATMENT AND FROM THE STUDY

Subjects may be discontinued from the investigational treatment in the following situations:

- Documented progression of disease or clinical progression
- Death
- Investigator discretion
- Non-compliance with study drug or protocol
- Important protocol deviation
- Pregnancy
- Patient discretion
- Withdrawal of consent (subjects are free to withdraw participation at any time)
- Lost to follow-up
- Subjects incorrectly initiated on study treatment
- Intercurrent illness that would, in the judgment of the investigator, affect assessments of clinical status to a significant degree
- Unacceptable toxicity
- Liver testing abnormalities meeting Hy's Law criteria (See Section 10.4.7)
- Study termination by the Sponsor

Subjects who are withdrawn from the study but are evaluable will not be replaced. Any subject who is withdrawn and is not evaluable may be replaced to ensure a minimum number of evaluable patients.

Subjects may withdraw from any aspect of the voluntary exploratory research at any time, without prejudice to further treatment and independent of any decision concerning participation in other aspects of the study.

If there is strong evidence of clinical benefit and reasons to justify continuation of the study drug, even though treatment discontinuation criteria have been met, this decision must be reviewed with the Sponsor, and continuation of therapy may be allowed assuming all other treatment resumption criteria have been met.

Subjects will be discontinued from the study in the following situations:

- Death
- Lost to follow-up
- Withdrawal of consent
- Study end per protocol
- Early study termination by Sponsor

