9.3 POPULATIONS FOR ANALYSES

Full Analysis Set (FAS)

The FAS includes all subjects who receive ≥ 1 dose of study drug. This analysis set will be used for subject characteristics and efficacy endpoints.

Safety Analysis Set

The Safety Analysis Set for this study will be the same as FAS as this study is not randomized. This analysis set will be used for safety endpoints, study treatment administration and post-study therapy.

DLT-Evaluable Analysis Set

The DLT-Evaluable Analysis Set includes all subjects in the Safety Analysis Set who take ≥ 24/28 scheduled Cycle 1 doses of ZN-c5 and/or the cumulative dose of palbociclib was ≥ 85% in Cycle 1 (or less, if for reasons due to DLTs) and underwent all treatment and safety procedures through Day 28 or experienced a DLT prior to Day 28. Determination of the MTD will be in the DLT-Evaluable Analysis Set.

Pharmacodynamic and Pharmacokinetic Analysis Sets

The Pharmacodynamic and PK Analysis Sets consist of all subjects in the FAS who have the necessary baseline and on-study measurements to provide interpretable results for the specific parameters of interest.

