6.5 Efficacy

6.5.1 Study Day and Visit Window Definitions

Study day is defined as the date of assessment – first date of treatment exposure + 1 for assessments that occur on or after the first date of treatment exposure; study day is defined as the date of assessment – first date of treatment exposure for assessments that occur prior to the first date of treatment exposure.

Tumor evaluations prior to first dose are assigned as baseline. Post dosing evaluations/responses during the treatment period will sequentially assigned based on chronology as Tumor Assessment 1, Tumor Assessment 2, etc. including any end of treatment assessments. Assessments collected during follow-up will be similarly assigned based on chronology as Follow-Up Assessment 1, Follow-Up Assessment 2, etc.

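### SAP 5.2 counts failures before the first assessment in the Combination Phase 2 futility set, but SAP 3.5.4 and the protocol still leave them out of the 19, and the design figures were not restated

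*SAP*

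**What the plan says.** The go rule is the same in protocol 6.1.8, protocol 9.2.4 and SAP 3.5.4: Stage 2 follows only if at least 11 of the first 19 evaluable subjects have clinical benefit. SAP Table 1 gives the mirror image, stopping at 10 of 19 or fewer. Who is evaluable differs by place.

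- **SAP 3.5.4** (and protocol 9.2.4 in the same words): "Subjects are evaluable for CBR if they have at least 1 post baseline disease/tumor assessment".
- **Protocol 6.1.8**, on which dose-escalation subjects may count towards Stage 1: "dosed subjects with at least 1 post baseline disease/tumor assessment [Section 9.3".
- **Protocol 9.3**, which these sentences cite, has no such definition. It offers only the Full Analysis Set (all dosed subjects) for efficacy: "This analysis set will be used for subject characteristics and efficacy endpoints".
- **SAP 5.2** starts from subjects with an evaluable post-baseline response assessment. It then adds those with progression, intolerable toxicity, death or discontinuation "prior to the first post-baseline assessment will also be considered evaluable and will be classified as non-responders". On its use it says: "This analysis set will be used for futility assessment in the Phase 2 combination".

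Protocol 7.2 bars replacement of withdrawn subjects who are evaluable, and then adds: "Any subject who is withdrawn and is not evaluable may be replaced to ensure a minimum number of evaluable patients".

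SAP 8 discloses the Tumor Response Evaluable Set as new. It does not mention the 19, the 51, the 10% evaluability loss, the 68% early stopping or the 80% power.

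**The concern.** One go/no-go rule has two denominators, and the conflict lies inside the SAP as well as between the SAP and the protocol. A subject who dies or stops before any scan is a failure among the 19 under SAP 5.2. Under SAP 3.5.4 that subject is not among the 19, and protocol 7.2 allows replacement. The narrower wording therefore lets early failures leave the futility count.

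The second difficulty concerns the design figures. The protocol gives one meaning of evaluable, then sets 50% against 70% in 51 evaluable subjects, and places the 10% loss outside the 51. Read together, this suggests rates among assessed subjects. Adding automatic failures to the set lowers the rate that the rule sees, so a regimen at the promising rate is stopped more often than planned.

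**Working it through.** **Inputs.** From protocol 9.2.4 and SAP 3.5.4: 19 subjects in Stage 1, 32 in Stage 2, 51 in all; continue at 11 or more of 19; poor rate 50%, promising rate 70%; one-sided alpha 2.5%; power 80%; early stopping 68%; about 10% evaluability loss, giving about 56 enrolled. Two inputs are not in the documents: the final success cutoff, which is inferred below, and the share d of dosed subjects who fail or leave without any assessment, which is assumed.

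**Formulas** (exact binomial, true rate p):

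- Stage 1 pass = P(X1 ≥ 11), with X1 ~ Bin(19, p). Early stopping = 1 − pass.
- Success with final cutoff c = sum over x = 11 to 19 of P(X1 = x) × P(X2 ≥ c − x), with X2 ~ Bin(32, p).

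**Step 1: reproduce the plan.** At p = 0.50, early stopping is 0.676, matching the stated 68%. For the final cutoff:

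| Success at | Alpha (p = 0.50) | Power (p = 0.70) |
|---|---|---|
| ≥32 of 51 | 0.039 | 0.851 |
| ≥33 of 51 | 0.022 | 0.801 |
| ≥34 of 51 | 0.011 | 0.729 |

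Only 33 of 51 meets both stated limits. Stage 1 pass at 70% is 0.916. For enrolment, 51 / 0.9 = 56.7, close to the stated 56, so the 10% does sit outside the 51.

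**Step 2: apply the SAP 5.2 set.** If 50% and 70% are rates among assessed subjects, and a share d is added as failures, the rates in the set become 0.50(1 − d) and 0.70(1 − d).

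| d (assumed) | Promising rate in set | Stage 1 pass | Power | Poor rate in set | Early stopping |
|---|---|---|---|---|---|
| 0% | 0.700 | 0.916 | 0.801 | 0.500 | 0.676 |
| 2% | 0.686 | 0.893 | 0.738 | 0.490 | 0.707 |
| 5% | 0.665 | 0.850 | 0.629 | 0.475 | 0.751 |
| 10% (upper bound) | 0.630 | 0.760 | 0.429 | 0.450 | 0.816 |

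**Step 3: the same effect as a head count.** At 70% among the rest, exactly one such failure among the 19 gives a pass probability of P(Bin(18, 0.7) ≥ 11) = 0.859. Two give P(Bin(17, 0.7) ≥ 11) = 0.775.

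**Step 4: how large d could be.** Protocol 1.3, footnote 16, limits it: "Applicable scans to be done at EOT visit if not done within the previous 4 weeks". SAP 6.5.1 numbers treatment-period assessments in sequence, "including any end of treatment assessments". Most subjects who stop early should therefore have one assessment. What remains is mainly early deaths, refusals, losses to follow-up and missed scans. The 10% row turns the whole stated evaluability loss into failures.

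**The case against.** The strongest reply is that the SAP has already chosen. SAP 5.2 names the set for the futility look, SAP 7 sends the interim to SAP 6.5.2, and SAP 6.5.2 repeats the non-responder rule. On this view SAP 3.5.4 is protocol sample-size text carried over and not updated. That stands as far as it goes: this is not an open choice between two rules of equal standing. It does not explain why SAP 3.5.4 still attaches the narrower definition to the rule, or why the 68% and 80% were carried over unchanged.

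The replacement worry is also partly answered. Once SAP 5.2 makes these subjects evaluable, the existing bar in protocol 7.2 covers them and no new rule is needed.

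Three stronger readings are tempting, and the documents do not support them.

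- A reader might infer the opposite error: rates that already count dropouts as failures, with the rule applied to assessed subjects only. At d = 10% this gives early stopping of 49% at the poor rate and alpha of about 11%. It needs the less supported reading of the rates and a rule that SAP 5.2 does not use.
- A reader might take the 43% power as the expected loss. No document gives the share of subjects without an assessment, and end-of-treatment scans should keep it well below 10%.
- A reader might say that the same patients give 11 of 19 under one definition and 10 of 19 under the other. That is inexact: excluding a dropout leaves 18 assessed subjects, and a further subject is needed to reach 19.

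Two limits on weight also stand. The futility criteria are described as guiding (protocol 9.4.7, SAP 3.4), and no formal test is planned (protocol 9.1, SAP 3.3), so power and alpha here are design figures. The part may also not have run. SAP 5.2 and SAP 7 make it conditional, SAP 6.6.3 splits adverse events by drug only for the Phase 1 combination, and the 18 May 2022 cut-off in SAP 8 precedes the SAP of 17 February 2023.

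**Conclusion.** The point holds as a contradiction in a go/no-go rule, with unadjusted design figures behind it. SAP 5.2 sets the futility denominator, while SAP 3.5.4 and the protocol still state a different one and cite a definition that protocol 9.3 does not contain.

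At an assumed dropout share of 2% to 5%, the loss is 2 to 7 percentage points in Stage 1 pass probability and 6 to 17 points in power at a true 70%. The power figures also rest on the inferred cutoff of 33 of 51. Both losses rest on 50% and 70% being rates among assessed subjects, which the design text suggests but does not state. If the rates were meant for the SAP 5.2 set, the stated 68% and 80% stand and only the wording needs alignment.

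Confidence is medium. The correction should be made, but its practical weight is limited because the part may not have been executed.

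**What to change.** 1. In SAP 3.5.4, replace the sentence that requires a post-baseline assessment with a reference to SAP 5.2. This also removes the empty citation of protocol 9.3 there.
2. In SAP 3.5.4 and Table 1, state that the 50% and 70% rates, the 68% early stopping and the 80% power assume rates in the SAP 5.2 set. If that was not the intention, restate the figures for that set, with the assumed share of subjects without an assessment and the final cutoff.
3. Restate what the 10% allowance behind 56 per cohort and 112 in total covers. Under SAP 5.2 this is mainly subjects still on treatment without an evaluable assessment.
4. In SAP 8, record the change of denominator from protocol 6.1.8 and 9.2.4, and note that protocol 9.3 lacks the definition they cite.

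If Combination Phase 2 was not executed, one sentence in SAP 7 or SAP 8 saying so replaces all four steps.

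The cost is SAP text only. No new data are needed, and 11 of 19 and 51 stay as they are.
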